### 3.2.3. Wireless motility capsule

- Wireless motility capsule (WMC) studies will reveal a subset of patients with gastroparesis who also have subtle or overt dysmotility of the small and/or large intestine which will adversely impact prognosis.
- WMC methods detect delays in gastric emptying in higher percentages of patients with suspected gastroparesis versus 4 hour gastric retention on scintigraphy. **Expectation:** We anticipate WMC will show delays in 60% of patients with symptoms suggestive of gastroparesis vs. in 40% with gastric scintigraphy based on data from initial trial of WMC in patients with prior scintigraphic demonstration of gastroparesis.
- Delays in small intestinal and/or colon transit are frequently observed in patients with symptoms suggestive of gastroparesis. **Expectation:** We anticipate WMC methods will detect delays in small intestinal transit in 20% and delays in colon transit in 50% of patients with suspected gastroparesis. Generalized transit delays in 2 or 3 regions (stomach, small intestine, colon) will be observed in 35% of patients with suspected gastroparesis based on data from prior published retrospective analysis of UMI and MGH databases.
- Different symptom profiles correlate with distinct gastric and extragastric motor defects.

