#### **Subhypotheses:**

- a. Fullness and early satiety severity correlates with delays in gastric emptying. **Expectations:** Postprandial fullness/early satiety subscale scores on the Gastroparesis Cardinal Symptom Index (GCSI) show progressive increases from normal WMC gastric emptying (<5 hr) to mildly delayed WMC gastric emptying (5-12 hr) to severely delayed WMC gastric emptying.
- b. Bloating and distention severity correlates with delays in small intestinal and colonic transit. **Expectations:** Bloating/visible distention subscale scores on the GCSI are greater in those with small bowel (SB) transit > 6 hr versus those with SB transit < 6 hr. Bloating/visible distention subscale scores also show progressive increases from normal WMC colon transit (<59 hr) to moderately delayed WMC colon transit (59-100 hr) to severely delayed WMC colon transit (>100 hr).
- c. Upper abdominal pain and discomfort correlate with abnormalities in pressure profiles in the stomach or small intestine. **Expectations:** Upper abdominal pain/discomfort subscale scores on the GCSI are greater in those with gastric contractions >29 and motility indices (MI) >9.82 in the hour before gastric emptying vs. in those with lower values. Upper abdominal pain/discomfort subscale scores are greater in those with elevated SB contractions and MI vs. in those with lower values.
- d. Symptom onset after meal ingestion and duration will correlate with the region of motor impairment. **Expectation:** Postprandial fullness/early satiety and upper abdominal pain/discomfort scores on visual analog scale (VAS) testing will begin earlier and resolve quicker as they derive predominantly from gastric dysfunction, whereas bloating and distention will peak later and persist longer due to their genesis in the small intestine and/or colon.

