**Screening visit 2:** Patients must discontinue use of proton pump inhibitors for 7 days, and stop histamine 2 antagonists, prokinetics, narcotics, anticholinergics, and cannabinoids for 3 days prior to this visit. If the patient normally takes insulin, they will be asked to take only half of their normal long-acting insulin. Record fasting glucose for diabetic patients; the blood glucose level must be checked to ensure it is less than 270 mg/dL to continue with the test. Patients will come to the center after fasting and will have a baseline electrogastrogram (EGG). Then they will eat a nutrient bar (SmartBar®) with water and swallow a wireless motility capsule (SmartPill®) with additional water, followed by a 90 minute EGG recording. Patients will continue to abstain from prokinetics, proton pump inhibitors, 'over the counter' laxatives, isotonic PEG electrolyte preparations (e.g. MiraLax), and prescription laxatives (e.g. lubiprostone) after ingesting the SmartPill® until they return for the follow-up visit in 4-7 days. These tests are described in detail in section [6.7.3](#). (All details of the EGG recording procedure, wireless motility capsule test, and specific questionnaires will be in the Standard Operating Procedures (SOP) manual.)

**Screening visit 3 (4-7 days after visit 2):** Record fasting glucose for diabetic patients; the blood glucose level must be checked to ensure it is less than 270 mg/dL to continue with the test. If the patient's blood glucose level is greater than 270 mg/dL, the EGG and water load test must be rescheduled for another day.

The study physician or coordinator will collect the SmartPill® receiver and download the data, and then the patient will undergo autonomic function testing to evaluate heart rate variability (see section [6.7.4](#)). Next the patient will have a 15 minute baseline electrogastrogram (EGG) and then complete a water load test, followed by a 30 minute EGG recording (this test is described in section [6.7.5](#)). Patients will have blood drawn for DNA and serum/plasma banking as the last procedure for the visit.

**Enrollment:** The GpR 2 data system will include software to check patient eligibility based on keyed

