After the baseline EGG recording is completed, the patient will begin the standard solid meal test by sitting up in the chair and ingesting one SmartBar® in a 10 minute period with 50 mL of room temperature water. It is expected that 100% of the bar will be ingested. The percentage of the SmartBar® that is consumed will be documented. After the SmartBar® is consumed; the SmartPill® will be ingested with another 50 ml of water and another visual analog scales symptoms sheet will be completed. The subject will then recline in the 30-45 degree position that they were in for the fasting baseline condition. The electrodes will be checked to verify that they are well adhered to the skin and the respiratory belt will be checked to verify it is snug before starting the EGG recording for the 90 minute postprandial period. Visual analog scales for stomach fullness, hunger, nausea, bloating, and abdominal discomfort will be completed at the 10, 20, 30, 60, and 90 minute time periods after ingestion of the SmartPill®. The patient may get out of the chair to stretch for 2 minutes at 30 and 60 minutes if necessary. At the 90 minute point the test is completed and the electrodes are removed. (Further details of the EGG recording and questionnaires will be in the SOP.)

Patients will be permitted to leave the study center after completion of the 90 minute EGG recording after SmartPill® ingestion. Study participants will leave with instructions to:

- 1) Remain fasting for 6 hours after SmartPill® ingestion; thereafter resume a normal diet; maintain a diary recording times of meal ingestion, bowel movements, and sleep; and keep the receiver in close proximity for 4-7 days. An event marker on the receiver will be depressed for diary entries.
- 2) Complete all remaining questionnaires for GpR 2: food questionnaire, nausea and vomiting questionnaire, neuropathy profile; abdominal pain questionnaire, state trait anxiety
- 3) Continue to abstain from prokinetics, proton pump inhibitors, and 'over the counter' laxatives, isotonic PEG electrolyte preparations (e.g. MiraLax), and prescription laxatives (e.g. lubiprostone) after ingesting the SmartPill® until they return for the follow-up visit
- 4) Return fasting for a follow-up visit 4-7 days after SmartPill® ingestion to return the receiver, questionnaires, and diaries for analysis.

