#### *SmartPill® transit and contractile parameters collected*

Gastric emptying will be calculated from time of ingestion to the time the capsule passes to the duodenum as defined by abrupt  $>2$  pH unit increases from the lowest postprandial value to  $>4$  that do not decrease to  $<4$  for  $>10$  minutes. Gastric emptying  $>5$  hr is considered delayed. Ileocecal passage

is defined when >1 pH unit decreases occur >30 min after gastric emptying; such pH decreases are noted in >95% of cases. Small bowel transit will be calculated from times of duodenal to ileocecal passage. Small bowel transit >6 hours is considered delayed. Anal expulsion is determined by 0.045°F/second temperature decreases. Colon transit will be calculated from times of ileocecal passage to anal expulsion. Colon transit >59 hours is considered delayed. Two pressure parameters will be computer calculated (MotilitGI, GIMS Data Viewer, SmartPill Corp., Buffalo, NY). Numbers of contractions >25 mmHg will be standardized to activity per 15 min to compare gastric, small bowel, and colon recordings of different length. Summed contractility measures >25 mmHg per 15 minutes will be provided by motility indices calculated as log (mmHg x min). Numbers of gastric contractions <29 and motility indices <9.82 in the hour before gastric emptying are considered abnormal.

Symptom profiles in those with isolated delayed gastric, small bowel, and colon transit as well as with generalized transit delays in >2 gut regions, and normal transit throughout. Symptoms will be compared in those with increased vs. normal vs. decreased contractile parameters in the same subsets. These studies will provide detailed characterizations of diffuse and generalized gut transit and contractile abnormalities in patients presenting with symptoms of gastroparesis.

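### The capsule receiver may come back at day 4 (96 h), which cannot record the planned colon transit class above 100 h, and a capsule not yet expelled gets no colon value

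*Protocol*

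**What the plan says.** - **Recording time.** Section 6.7.3 (Test protocol) has the patient "keep the receiver in close proximity for 4-7 days" and come back in that window after "ingestion to return the receiver, questionnaires, and diaries for analysis".
- **Collection.** Section 6.2 sets "Screening visit 3 (4-7 days after visit 2") and has staff collect the "receiver and download the data, and then the patient will undergo autonomic function testing".
- **Calculation rule.** Section 6.7.3 (SmartPill transit and contractile parameters) states: "Colon transit will be calculated from times of ileocecal passage to anal expulsion". Expulsion is identified from a temperature fall on the recording. Colon transit above 59 h counts as delayed. The corresponding limits are 5 h for gastric emptying and 6 h for small-bowel transit.
- **Planned classes.** Section 3.2.3, subhypothesis (b), expects bloating scores to rise from normal colon transit (below 59 h) to "moderately delayed WMC colon transit (59-100 hr") to "severely delayed WMC colon transit (>100 hr").
- **Expected rates.** Section 3.2.3 anticipates "delays in colon transit in 50% of patients with suspected gastroparesis", and generalized delay in two or three regions in 35%.
- **Capsule not yet passed.** Section 6.7.3 says expulsion will be asked about and a second follow-up arranged if needed, with retention procedures after 14 days. It does not say that the receiver is kept or reissued.

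**The concern.** The shortest permitted recording is shorter than the transit time that defines the top class. Gastric and small-bowel time are also spent before the colon clock starts. The population is selected for symptoms of slow gastric emptying, so this upstream time will often be long.

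The calculation rule adds a second problem. Without a recorded expulsion there is no end point and hence no value, even when the trace already shows more than 59 h in the colon. Whether a value exists then depends on the quantity being measured and on an administrative choice, the booked return day. At stake are the upper end of the bloating gradient in subhypothesis (b) and, depending on how unexpelled capsules are handled, the colon and generalized delay rates. The capsule test is done at baseline only, so a lost value is not measured again later.

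**Working it through.** The Protocol gives no figure to reproduce here. The check is direct arithmetic on its own limits.

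**Inputs.** Return at day 4, 5, 6 or 7 (Sections 6.2 and 6.7.3), taken as 24 h per day because ingestion follows an overnight fast in the morning and the return visit is also fasting. Upstream time is gastric emptying plus small-bowel transit:
- 0 h, as an absolute bound
- 5 + 6 = 11 h, the upper normal limits in Section 6.7.3
- 12 + 6 = 18 h, where 12 h is the top of the mildly delayed gastric class in subhypothesis (a)
- 24 + 6 = 30 h, where the 24 h gastric time is an assumption

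**Formula 1.** Longest recordable colon transit = 24 × return day − upstream time.

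| Return day | Hours recorded | 0 h upstream | 11 h | 18 h | 30 h (assumed) |
|---|---|---|---|---|---|
| 4 | 96 | 96 | 85 | 78 | 66 |
| 5 | 120 | 120 | 109 | 102 | 90 |
| 6 | 144 | 144 | 133 | 126 | 114 |
| 7 | 168 | 168 | 157 | 150 | 138 |

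At day 4 no entry exceeds 100 h, even with zero upstream time. The upper part of the 59-100 h class is cut off too. At day 5 the top class is out of reach once upstream time reaches 120 − 100 = 20 h.

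**Formula 2.** Receiver time needed to see more than 100 h = 100 h + upstream time.
- 0 h upstream: more than 100 h (4.17 days)
- 11 h: more than 111 h (4.63 days)
- 18 h: more than 118 h (4.92 days)

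All exceed 96 h. Booking the day-4 visit later in the day does not remove the gap: with 11 h upstream it would need to be more than 111 − 96 = 15 h later.

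**Delayed versus not delayed.** A trace with no expulsion still proves delay once the time since ileocecal passage exceeds 59 h. At day 4 that holds for upstream time below 96 − 59 = 37 h, which covers every cell in the table. The information exists, but the literal calculation rule does not use it.

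**Direction of bias if unexpelled patients were dropped.** Suppose a share d of all patients is truly delayed but has no value, and the true rate is the anticipated 50%. The observed rate is then (0.50 − d)/(1 − d). For assumed d of 5%, 10% and 15% this gives 0.45/0.95 = 47%, 0.40/0.90 = 44% and 0.35/0.85 = 41%. These values of d are illustrations only. The Protocol gives no distribution of return days or of colon transit from which d could be derived.

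**The case against.** The strongest reply is that the remedy belongs elsewhere. Section 7 requires every proposal to specify its missing-data methods, and Section 6.2 leaves capsule test details to an SOP that is not at hand. Either could supply a censoring rule. This stands in part: a missing analysis rule alone would not be a finding. But the return window, the class above 100 h and the calculation to expulsion are all fixed in the Protocol, and no later analysis can recover hours that were not recorded.

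A second reply is that the arranged second follow-up might extend recording. The text is silent on the receiver, so this cannot be excluded. As written, however, the receiver has already been handed in and downloaded at the 4-7 day visit.

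A third reply concerns importance, and it stands. The class above 100 h serves part of one of four capsule subhypotheses, in a baseline-only test that Section 6.2 allows enrolled patients to miss.

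A reader might also infer more than the text supports:
- **That the top class is lost.** It is not. Returns at days 6 and 7, and at day 5 with upstream time under 20 h, can reach it.
- **That the 50% and 35% rates are biased low.** Nothing in the Protocol says unexpelled patients are dropped. Both figures are prior expectations rather than registry estimates. A patient delayed in stomach and small bowel counts as generalized delay whatever the colon result.

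**Conclusion.** The point holds in limited form. The 4-day lower limit on receiver return is incompatible with observing the class above 100 h. At day 4 this needs no assumption beyond 24 h per day; at day 5 it applies when upstream time is 20 h or more. Under the literal calculation rule, a capsule not expelled by receiver return gets no colon transit value, so missingness depends on slow transit and on the return day.

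The top class is thinned by an amount the documents do not allow to be computed. The colon-delay rate, and the generalized-delay rate where the colon result decides it, would be biased low only if such patients were dropped. The size of that bias cannot be computed either. Delayed versus not delayed remains assignable in most cases, provided the recorded time since ileocecal passage is used.

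**What to change.** In Section 6.7.3 (SmartPill transit and contractile parameters), add a rule for recordings with no expulsion by receiver return:

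- Treat colon transit as right-censored at the time recorded since ileocecal passage.
- Count the patient as delayed once that time exceeds 59 h, and as above 100 h once it exceeds 100 h.
- Keep these patients in the denominator. In the subhypothesis (b) comparison, class those censored between 59 and 100 h as delayed with severity unknown.
- Record the date and time of receiver return.

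Separately, reconcile the 4-day lower limit in Sections 6.2 and 6.7.3 with the class above 100 h in Section 3.2.3. Abstention from prokinetics, proton pump inhibitors and laxatives runs until the same visit, so any change to the window also changes its length. Which passage should give way is for the investigators.

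The analysis rule costs some wording and one recorded time, with no extra visit or test. The downside is that some patients will have delay of unknown severity. The rule also gives no lower bound when ileocecal passage was not identified; the Protocol says the marking pH fall is seen in more than 95% of cases. Any change to the return window would carry its own burden, which this estimate does not include.

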#### *SmartPill® transit and contractile parameters collected*

Gastric emptying will be calculated from time of ingestion to the time the capsule passes to the duodenum as defined by abrupt  $>2$  pH unit increases from the lowest postprandial value to  $>4$  that do not decrease to  $<4$  for  $>10$  minutes. Gastric emptying  $>5$  hr is considered delayed. Ileocecal passage

is defined when >1 pH unit decreases occur >30 min after gastric emptying; such pH decreases are noted in >95% of cases. Small bowel transit will be calculated from times of duodenal to ileocecal passage. Small bowel transit >6 hours is considered delayed. Anal expulsion is determined by 0.045°F/second temperature decreases. Colon transit will be calculated from times of ileocecal passage to anal expulsion. Colon transit >59 hours is considered delayed. Two pressure parameters will be computer calculated (MotilitGI, GIMS Data Viewer, SmartPill Corp., Buffalo, NY). Numbers of contractions >25 mmHg will be standardized to activity per 15 min to compare gastric, small bowel, and colon recordings of different length. Summed contractility measures >25 mmHg per 15 minutes will be provided by motility indices calculated as log (mmHg x min). Numbers of gastric contractions <29 and motility indices <9.82 in the hour before gastric emptying are considered abnormal.

Symptom profiles in those with isolated delayed gastric, small bowel, and colon transit as well as with generalized transit delays in >2 gut regions, and normal transit throughout. Symptoms will be compared in those with increased vs. normal vs. decreased contractile parameters in the same subsets. These studies will provide detailed characterizations of diffuse and generalized gut transit and contractile abnormalities in patients presenting with symptoms of gastroparesis.

#### 6.7.4. Autonomic function testing

Using the ANSAR ANX 3.0 system, the patient will undergo six challenges to evaluate sympathetic and parasympathetic function. The test consists of:

- 1) a five minute, resting, initial baseline,
- 2) a one minute parasympathetic challenge of paced, rhythmic, deep breathing,
- 3) a one minute (second) baseline – the Valsalva baseline,
- 4) a 1:35 minute Valsalva challenge, which consists of a series of five short Valsalvas (no more than 15 seconds in duration) with short rests in between each,
- 5) a two minute (third) baseline – the stand baseline, and
- 6) a five minute postural change (stand) challenge which consists of a rapid change in posture, followed by approximately five minutes of quiet upright posture.

The system records the patient's electrocardiogram (ECG) blood pressure (BP) and heart rate responses to evaluate sympathetic and parasympathetic function.

#### 6.7.5. EGG and water load test protocol:

For each EGG and water load test, the clinical center needs to have a cup that has a 50 mL measured mark for water, 3 EGG leads, a dedicated quiet area for the EGG recording, a reclining chair, a blanket and the 3CPM EGG equipment and software.

#### *Test protocol*

On the morning of the EGG and water load satiety test, the patient will arrive fasting. Patients may take their usual medications with a small amount of water (up to 4 oz) up to two hours prior to the study, but should refrain from coffee, tea, or juice. After arriving to the clinic, the patient's blood glucose level must be checked to ensure it is less than 270 mg/dL. If the patient's blood glucose level is greater than 270 mg/dL the EGG and water load satiety test must be rescheduled for another day.

Baseline symptoms prior to EGG recording will be obtained using visual analog scales for stomach fullness, hunger, nausea, bloating, and abdominal discomfort. The subject will mark each symptom line with a vertical line to indicate how they currently feel in terms of that symptom. Once the EGG and respiratory signals are stable, the baseline EGG recording period can begin. Patients will undergo a 15 minute baseline EGG in a reclining chair with the subject positioned at a 30-45 degree tilt.

Patients will begin the Water Load Satiety Test. For this, participants will sit upright. During the test, participants will drink cool water for a 5 minute period until they feel "**completely full.**" The total volume of water consumed will be recorded.

A continuous 30 minute EGG recording is then obtained. The patient's symptoms are recorded using VAS at 10, 20, and 30 minutes after ingestion of the water (at the end of the 0-10 minute, 11-20 minute, and the 21-30 minute post-satiety periods). The test is completed after the 30 minute recording period and the electrodes are removed. (Complete details will be contained in the SOP.)

#### 6.7.6. Standardized questionnaires

Several standardized questionnaires will be administered at baseline (prior to enrollment) and during follow-up at specified intervals (see Appendix [11.2](#) for the data collection schedule). The purpose of the questionnaires is to obtain important information regarding gastroparesis symptoms, nutrition, pain, and health-related quality of life.

**Patient Assessment of Upper Gastrointestinal Disorders-Symptoms (PAGI-SYM).** The self-reported questionnaire is composed of 20 items and 6 subscales. The severity of each symptom item over a 2-week recall period is scored from 0 (none or absent) to 5 (very severe). The GCSI, a 9 symptom survey relevant to gastroparesis stratified in 3 subscales—nausea/vomiting, fullness/early satiety, and bloating, is contained in the PAGI-SYM. The GCSI correlates with patient severity ratings and is responsive to changes in overall symptoms. Two additional items for constipation and diarrhea also will be recorded and scored and their main symptom will be determined.

**Patient Assessment of Upper Gastrointestinal Disorders-Quality of Life (PAGI-QoL).** A validated 30 item questionnaire to assess quality of life in patients with dyspepsia, GERD, or gastroparesis. Copyright© 2004 Johnson & Johnson.

**Rome III Diagnostic Questionnaire for Adult Functional GI Disorders.** The Rome Foundation has developed a 93 item diagnostic questionnaire to assist physicians, health care professionals and researchers in identifying individuals who have one or more functional gastrointestinal disorders (FGIDs). Rome III modules for (1) nausea, vomiting, and belching and (2) functional dyspepsia to assess upper symptoms and (3) functional bowel disorders to assess lower symptoms are validated surveys from the Rome Foundation to quantify symptoms and suggest functional disorders involving the upper or lower gut. Copyright© 2006 by Douglas A. Drossman, Enrico Corazzari, Michel Delvaux, Robin C. Spiller, Nicholas J. Talley, W. Grant Thompson, William E. Whitehead.

**Beck Depression Inventory, Second Edition (BDI-II).** The BDI-II is a commonly used, reliable 21-item self-report measure designed to assess for depression.

**State Trait Anxiety Inventory.** The STAI is a 40-item self-report measure designed to assess both situational and characterological anxiety. This measure provides two subscale scores (State and Trait) and has been shown to exhibit good reliability and internal consistency.

**Patient Health Questionnaire (PHQ-15).** The PHQ-15 is a brief, self-administered questionnaire that may be useful in screening for somatization and in monitoring somatic symptom severity in clinical practice and research.

**Brief Pain Inventory (BPI).** Developed in 1989 by [name] for rapid assessment of the severity and impact of pain in cancer patients. The BPI has since been translated into more than two dozen languages, and is widely used in both research and clinical settings.

**SF-36 Health Survey (SF-36).** The SF-36 is a 36-item, self-report measure designed to assess quality of life in patients. This measure also provides two summary scores (physical and mental health) and eight scale scores. It is reliable and internally consistent.

**Neuropathy Total Symptom Score (NTSS-6).** The NTSS-6 provides a valid assessment of neuropathy sensory symptoms in patients with diabetes.

**Block 2005 Food Frequency Questionnaire.** This full-length (approximately 110 food item) questionnaire was designed to estimate usual and customary intake of a wide array of nutrients and food groups. It takes 30-40 minutes to complete and is intended for either self- or interviewer-administration. The food list was developed from NHANES 1999-2002 dietary recall data; the nutrient database was developed from the USDA Food and Nutrient Database for Dietary Studies (FNDDS), version 1.0. A series of "adjustment" questions provide greater accuracy in assessing fat and carbohydrate intake. Individual portion size is asked for each food, and pictures are provided to enhance accuracy of quantification. Copyright 2005 ©Block Dietary Data Systems  
[www.nutritionquest.com](http://www.nutritionquest.com).

**Block Energy Expenditure Survey.** This tool is designed to measure total average energy expenditure per day, as well as minutes per day of moderate and vigorous activities, and average MET-minutes by activity type. The form assesses job type and time, frequency and duration of the 26 most relevant daily-life and leisure time activities as determined by analysis of the Human Activities Patterns Survey data. It takes 20-25 minutes to complete.

**Nausea Profile and Vomiting questionnaire.** The nausea profile (NP) is a subjective symptom checklist with the goal of obtaining a more in-depth description of what patients are experiencing when they report the feeling of nausea. The NP evaluates the experience of 3 dimensions which are involved in the complex feeling of nausea, somatic distress, GI distress and emotional distress.

**GpCRC abdominal pain questionnaire.** The consortium developed a questionnaire to address abdominal pain in gastroparesis patients.

